## **STUDY PROCEDURES**

### **Schedule of events**

	Screen (using SOC in last 48hr	Baseline Screening and baseline may be combined if labs are done								Weeks		
Week		1	1	1	1	1	1	1-2	3	4	5	6
Day		0	1	2	3	4	5	6- 14	21	28	35	42
Window (hrs) +/-				6	6	6	6	24	48	48	48	48
Informed consent	x											
SARS CoV-2	x											
EKG	x											
Medication review	x											
Complete blood count, comprehensive metabolic panel and magnesium	x											
History of Glucose- 6 phosphate- dehydrogenase	x											

(G6PD) deficiency assessment												
(G6PD) lab (*research if preformed)	x*											
Determine eligibility		x										
Pregnancy test Unless SOC within 7-14 days	x											
Study drug		x	x	x	x	x	x					
Review medical record**	x	x	x	x	x	x	x	x	x	x	x	x
Adverse Drug Reaction Collection			x	x	x	x	x	x	x	x	x	x
Symptom screen		x	x	x	x	x	x	x	x	x	x	x
Temperature ( from medical record taken and recorded by participant while at home*)		x	x*	x*	x*	x*	x*	x*				

\* thermometer at home and log

\*\* medical history, study outcomes, AEs, SAEs

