## **STUDY AIMS/ENDPOINTS**

### **Primary**

1. Time (hours) from randomization to recovery defined as 1) absence of fever, as defined as at least 48 hours since last temperature  $\geq 38.0^{\circ}\text{C}$  without the use of fever-reducing medications AND 2) absence of symptoms of greater than mild severity for 24 hours AND 3) not requiring supplemental oxygen beyond pre-COVID baseline AND 4) freedom from mechanical ventilation or death

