### **Secondary**

1. Time to resolution of fever defined as at least 48 hours since last temperature  $\geq 38.0^{\circ}\text{C}$  without the use of fever-reducing medications

2. Time to improvement in symptoms (scored as mild or absent and remained so for 24 hour)
3. Mean improvement in symptom from baseline
4. Duration of hospitalization
5. Proportion requiring supplementary oxygen (above baseline usage) at any time during follow-up
6. Duration (days) of requirement for supplementary oxygen
7. Proportion requiring ICU admission at any time during follow-up
8. Proportion requiring mechanical ventilation at any time during follow-up
9. Ventilator free days
10. All-cause mortality

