### Enrollment

Hospitalized patients with documented SARS CoV-2 infection will be screened for study eligibility. If eligible, consenting participants will be randomized to one of the four arms. Up to 125 participants will be recruited for each of the study groups, with a planned total enrollment of 500 participants. Participants will be randomized to either one of the following arms in a 1:1:1:1 manner. Drugs will be provided by the BJC investigational pharmacy using standardized Epic order sets. If participants are discharged, we will coordinate with the investigational pharmacy services to ensure that participants receive the full course of therapy.

**Arm 1:** Hydroxychloroquine 400mg orally twice a day for one day, followed by 200mg twice a day for four consecutive days (Five days in total). The drug will be supplied in 200mg tablets.

**Arm 2:** Hydroxychloroquine 400mg orally twice a day for one day, followed by 200mg twice a day for four consecutive days (Five days in total). The drug will be supplied in 200mg tablets.  
AND

[figure not shown]
Azithromycin 500mg orally once, followed by 250mg daily for four consecutive days (five days total). The drug will be supplied in 250mg tablets.

**Arm 3:** Chloroquine phosphate 1000mg orally once, followed in 12 hours by 500mg, then 500mg orally twice daily for 4 days (Five days in total). The drug will be supplied in 500mg tablets.

**Arm 4:** Chloroquine phosphate 1000mg orally once, followed in 12 hours by 500mg, then 500mg orally twice daily for 4 days (Five days in total). The drug will be supplied in 500mg tablets.

AND

Azithromycin 500mg orally once, followed by 250mg daily for 4 consecutive days (5 days total). The drug will be supplied in 250mg tablets.

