### Follow up

Participants will be asked to complete daily symptom surveys for 14 days from randomization, then weekly thereafter for 4 weeks resulting in a total duration of follow up of 42 days. During hospitalization, daily symptom surveys will be completed in conjunction with the study coordinators via telephone. On discharge participants will have the option to complete electronic symptom surveys or complete symptom surveys via telephone with study coordinator. In the event that the participant opts for electronic symptom surveys on discharge they will also

receive a follow up call from a study coordinator every 7 days during the initial 14 day period. In addition, failure to submit a symptom survey will prompt a study follow up call.

On discharge from hospital in addition to completing daily symptom surveys participants will be asked to take and record their temperature twice daily with extra recordings performed if concern for fever onset.

Symptoms will be collected using the Flu-PRO scale (appendix 1) validated for use in influenza as at present validated tools for COVID-19 are not available.

To assure safety and protocol adherence phone calls to participants will be initiated if there is no contact at the designated time points.

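### For participants at home, temperature after day 14 and antipyretic use after discharge are not clearly scheduled, although dating the primary endpoint needs both

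*Combined protocol and SAP*

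**What the plan says.** - **Endpoint.** Under Study Aims/Endpoints, recovery is four conditions joined by AND. The fever condition is 48 hours since the last temperature of 38.0 °C or above, and it holds only "without the use of fever-reducing medications AND 2) absence of symptoms of greater than mild severity for 24 hours". The first secondary endpoint rests on the same fever rule ("Time to resolution of fever defined as at least 48 hours since last temperature").
- **Follow-up.** The Primary endpoint analysis section censors unrecovered participants at 42 days, so a recovery on days 15-42 is a primary event.
- **Schedule of events.** The row "Temperature ( from medical record taken and recorded by participant while at home" is marked for day 0, days 1-5 and days 6-14, and is blank for days 21, 28, 35 and 42. Symptom screen, adverse drug reaction collection and record review are all marked through day 42. Medication review is marked at screening only. The home source of temperature is described as "thermometer at home and log", and the record-review footnote lists "medical history, study outcomes, AEs, SAEs".
- **Follow up.** "On discharge from hospital in addition to completing daily symptom surveys participants will be asked to take and record their temperature twice daily", with no end day. On the surveys: "Participants will be asked to complete daily symptom surveys for 14 days from randomization, then weekly thereafter for 4 weeks".
- **Discharge.** The Enrollment section provides for discharge before the five-day course ends: "If participants are discharged, we will coordinate with the investigational pharmacy services to ensure that participants receive the full course of therapy".

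**The concern.** The temperature row stops while the rows around it continue. The Follow up text can be read in two ways. If home temperatures run with the daily surveys that the sentence mentions, they end at day 14 and a participant still febrile at home has no scheduled reading from which to date recovery. If they are open-ended, the text contradicts the blank cells. Staff who follow the table as written would stop collecting at day 14.

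The antipyretic condition raises a separate question, and it starts at discharge rather than at day 14. A participant at home whose fever is suppressed by medication, and for whom fever is the last unmet criterion, could be scored as recovered unless something records the medication. No visible passage says that anything does.

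At stake is whether the primary event is classified correctly. Readings and medication use that were never recorded cannot be restored at analysis.

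**Working it through.** **Inputs from the Sample size and power analysis section:** median recovery 11 days (non-AZM) and 7 days (AZM), censoring 0.04 per day, 125 per arm. Follow-up of 42 days and the two-sided 0.05 level come from the Primary endpoint analysis section.

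**Step 1: reproduce the stated power.** With exponential times, the recovery hazards are λ = ln 2/11 = 0.0630 and ln 2/7 = 0.0990 per day, and c = 0.04. Expected recoveries per arm by day t are 125 × λ/(λ+c) × (1 − exp(−(λ+c)t)).
- By day 42: 75.5 + 88.8 = 164.2 per comparison.
- Power = Φ(ln(11/7) × √164.2 / 2 − 1.96) = Φ(0.936) = 82.5%, against the plan's 82%. The plan's figure is reproduced.

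**Step 2: recoveries after day 14.** By day 14 the same formula gives 134.7. The remainder is 17.1 (non-AZM) + 12.5 (AZM) = 29.5, or 29.5/164.2 = 18%. Unrecovered and uncensored at day 14: 125 × exp(−(λ+c) × 14) = 29.6 + 17.9 = 47.4 per comparison, about 95 over both comparisons.

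**Step 3: how many of these hinge on fever.** This needs assumptions that the documents do not supply:
- Fever times are exponential and everyone is febrile at entry.
- Fever median is 7 days without AZM (the plan's starting figure) and about 4.5 days with AZM (7 × 7/11, keeping the plan's ratio).
- The febrile share among late recoveries equals that among the unrecovered at day 14.

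Febrile share of the unrecovered at day 14:
- Non-AZM: 0.250/0.414 = 0.604.
- AZM: 0.116/0.250 = 0.463.

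Exposed late recoveries: 0.604 × 17.1 + 0.463 × 12.5 = 16.1 per comparison.

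**Step 4: effect on power.** Inpatient temperatures are in the chart, so only the share p at home is exposed. The documents do not give p. Treating every exposed recovery at home as lost, power = Φ(ln(11/7) × √(164.2 − p × L)/2 − 1.96).

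| Share at home (p) | All febrile at entry, L = 16.1 | Half febrile at entry, L = 8.0 |
|---|---|---|
| 0 | 82.5% | 82.5% |
| 10% | 82.2% | 82.4% |
| 25% | 81.6% | 82.1% |
| 50% | 80.6% | 81.6% |

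The second column matters because fever is not an inclusion criterion.

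**Step 5: the antipyretic condition.** No arithmetic is possible: the documents give neither the rate of antipyretic use at home nor the time of discharge.

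**The case against.** The other side has four fair points.

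- **The Follow up text has no stop day.** Read plainly, it could run to day 42. This stands as far as it goes: what is secure is that the text and the table must be reconciled. A reader might infer that readings after day 14 will be missing, but the documents do not establish that.
- **Silence is not absence.** The home log and case report forms are not in the documents. Appendix 1 shows 17 items, while the maximum score of 20 in the Primary endpoint analysis section (fever plus items) implies 19, so the questionnaire may be cut short in the text available. It would therefore be too strong to say that the trial does not record antipyretics. What can be said is that no visible passage schedules it.
- **Record review of study outcomes runs to day 42, and coordinators telephone participants.** This answers the point for inpatients. For participants at home, the schedule itself names a participant log as the temperature source, and nothing says that home antipyretic use reaches the medical record.
- **Few participants are affected.** For late temperatures this is right. A reader might be tempted to count all 29.5 late recoveries as lost, which leaves 134.7 events and 74.6% power. The documents do not support that, because inpatients have charted temperatures and fever is only one of four criteria. Nor is it consistent to give the AZM arm a 7-day median for both fever and recovery: the sample size section says that recovery adds requirements to the settling of fever.

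Nothing in the documents suggests that either gap differs between arms, and none is claimed here.

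**Conclusion.** The point holds as a low-cost improvement. The Schedule of events and the Follow up section conflict, or else leave home temperatures on days 15-42 uncovered. Recording of antipyretic use at home is not visibly planned, although the endpoint definition depends on it. The first secondary endpoint is affected in the same way.

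The effect on power is small: about two percentage points if half of some 16 exposed recoveries are at home, and about half that loss if half of participants are febrile at entry. These figures rest on the assumed exponential fever times, the assumed 4.5-day fever median with AZM, and the loss of every exposed recovery at home. The actual share at home and the effect of antipyretic use cannot be sized from the documents. The plan's 82% power is not in error. The reason to act is correct classification of the primary event.

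**What to change.** 1. **Reconcile the table and the text.** Extend the temperature row to day 42 and state the stop day in the Follow up section. Participants at home would continue the existing twice-daily log to day 42, or to a stop point set by a fixed rule on logged data. The stop should not depend on someone judging recovery in real time, because the trial is open-label.
2. **Record antipyretic use.** Add to the home log from discharge, or confirm that it already holds, one yes/no item on fever-reducing medication in the past 24 hours. State in the analysis section that time covered by a yes does not count toward the 48 hours, as the endpoint definition implies. For inpatients, take temperature and antipyretic use from the chart.

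**Cost.** This is a small amendment, since the thermometer and log are already in use. The extra logging after day 14 falls on about 95 of 500 participants (those unrecovered, on the plan's assumptions), or on more if everyone at home logs to day 42.

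**Limit.** Symptoms are surveyed only weekly after day 14, and the symptom criterion is part of the same endpoint. The change improves classification of fever status, but late recovery dates stay coarse.

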### Pregnancy Test

Unless done as SOC within the last 7-14 days prior to entry a negative  $\beta$ -HCG (human chorionic gonadotropin) pregnancy test (urine or serum) on day of enrollment for women presumed to be of reproductive will be done.

### Eligibility

Participants hospitalized with SARS CoV-2 infection who meet the inclusion/exclusion criterion will be enrolled. Standard of care investigations including laboratory test (complete blood count, comprehensive metabolic panel, magnesium, and glucose-6-phosphate dehydrogenase) and ECG performed within 48 hours will be used to determine study eligibility.

### Baseline assessment

Eligible participants will be consented and randomized according to the procedure outlined above. Demographics and clinical parameters will be recorded

### Follow up

Participants will be asked to complete daily symptom surveys for 14 days from randomization, then weekly thereafter for 4 weeks resulting in a total duration of follow up of 42 days. During hospitalization, daily symptom surveys will be completed in conjunction with the study coordinators via telephone. On discharge participants will have the option to complete electronic symptom surveys or complete symptom surveys via telephone with study coordinator. In the event that the participant opts for electronic symptom surveys on discharge they will also

receive a follow up call from a study coordinator every 7 days during the initial 14 day period. In addition, failure to submit a symptom survey will prompt a study follow up call.

On discharge from hospital in addition to completing daily symptom surveys participants will be asked to take and record their temperature twice daily with extra recordings performed if concern for fever onset.

Symptoms will be collected using the Flu-PRO scale (appendix 1) validated for use in influenza as at present validated tools for COVID-19 are not available.

To assure safety and protocol adherence phone calls to participants will be initiated if there is no contact at the designated time points.

#### **End of study visit**

The final study visit will via telephone at 6 weeks post enrollment

#### **Study Duration**

Total duration of participation in the study should not exceed 6 weeks

### **SAFETY ASSESSMENTS**

#### **ADVERSE EVENTS AND STUDY MONITORING**

Definition of Adverse Events

Adverse Event (AE)

An Adverse Event is any untoward medical occurrence observed in a patient that develops or worsens from baseline status in association with a subject's participation in the research, whether considered research-related or not. An AE can therefore be any unfavorable and unintended sign (including an abnormal laboratory finding), symptom, disease, or injury temporally associated with the research, whether or not considered related to the research.

Serious Adverse Event (SAE)

A Serious Adverse Event is any AE that results in any of the following outcomes:

- Death
- A congenital anomaly, birth defect, or cancer in a baby born to a female subject
- Life-threatening adverse experience (places the subject at immediate risk of death from the event as it occurred)
- Inpatient hospitalization or prolongation of existing hospitalization
- Persistent or significant disability/incapacity
- Based on appropriate medical judgment, may jeopardize the subject's health and may require medical or surgical intervention to prevent one of the other outcomes listed in this definition

### Adverse Drug Effect (ADE)

An Adverse Drug Effect is an AE that is definitely, probably, or possibly related to the use of study drug

### Unexpected Adverse Drug Effect (UADE)

An Unexpected Adverse Drug Effect is any serious adverse effect on health or safety, or any life-threatening problem or death caused by, or associated with study drug, if that effect, problem, or death was not previously identified in nature, severity, or degree of incidence in the investigational plan or application; or any other unanticipated serious problem associated with a drug that relates to the rights, safety, or welfare of study participants.

### Outcome

The clinical course of all AEs should be followed until a medical outcome is determined. The clinical outcome of all AEs will be recorded as follows:

- Fatal
- Not Yet Recovered (Patient did not recover and symptoms/sequelae continue)
- Recovered (Patient returned to baseline status)
- Recovered with Sequelae (Patient recovered but with clinical sequelae from the event)
- Unknown

### Adverse Event Collection Requirements for this protocol

All AEs must be recorded on the eCRFs if any of the following criteria have been met.

- All Grade  $\geq 2$  AEs
- All AEs that led to a change in study treatment regardless of grade
- All AEs meeting SAE definition
- Started within 7 days after the last dose of study drug

All AEs that are reported must have their severity graded. To grade AEs, refer to the Division of AIDS Table for Grading the Severity of Adult and Pediatric Adverse Events (DAIDS AE Grading Table), corrected Version 2.1, July 2017.

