### Reporting Requirements

Adverse events must be reported by study personnel into the Redcap system using the electronic case report forms within 3 days of their knowledge of the occurrence. Investigators are responsible for following all relevant local IRB policies and procedures. The Principal Investigator will follow IRB policy in terms of reporting adverse events.

Serious Adverse Events that occur within 6 weeks after randomization must be reported by the site investigator or personnel into the Redcap system on the Serious Adverse Event CRF within 1 working day after the site investigator or personnel first learn of the event.

For SAEs, the Principal Investigator will review the report and obtain any needed additional clarifications concerning the event by direct telephone conversations and/or e-mail with the involved providers. The investigator's description and categorization of the event, and additional relevant information, will then be reviewed by the study's Safety Officer. The Safety Officer will determine if the event was properly categorized. If not, he will provide the Principal Investigator with a modified categorization, along with a brief written rationale for re-categorizing the event. In nearly all instances, the Safety Officer's categorization will be considered the final categorization of the event.

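### The seven-day post-dose bullet sits in an any-of-four list, so ordinary grade 1 adverse events are recorded just after dosing but not during it

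*Combined protocol and SAP*

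**What the plan says.** The section Adverse Event Collection Requirements for this protocol gives the recording rule: "All AEs must be recorded on the eCRFs if any of the following criteria have been met". Four bullets follow. The first covers events of grade 2 or higher. The second is "All AEs that led to a change in study treatment regardless of grade" and the third is "All AEs meeting SAE definition". The fourth is "Started within 7 days after the last dose of study drug". The first three carry no time limit, and the fourth carries no grade. Nothing else in the document says how the fourth combines with the others.

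Two other places bear on the period of collection:

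- **Schedule of events.** The row "Adverse Drug Reaction Collection" is marked from Day 1 to Day 42. The medical record review row is marked in every column to Day 42, and its footnote reads "medical history, study outcomes, AEs, SAEs".
- **Reporting Requirements.** "Serious Adverse Events that occur within 6 weeks after randomization must be reported" by the site into the study database.

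**The concern.** A time window placed in a list joined by *any* does not limit anything. It admits further events. Here it admits events of every grade for one week, and that week begins when exposure ends. The grade threshold is thus waived after treatment and applied during it, the reverse of what one would want for describing tolerability.

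A site that notices this may instead treat the bullet as a cut-off for the other three. That gives a different safety dataset and cuts across the schedule. The trial is open-label, so staff who know the arm would be choosing how to apply an unclear rule.

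The IDSMB is asked to review adverse events and to confirm that the dosing regimen is safe and suitable. The plan does not say which tabulations it will receive, but the eCRF is the adverse event record that the protocol describes. What is at stake is whether mild toxicity is counted on a consistent basis and, on the other reading, whether later non-serious events are counted at all.

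**Working it through.** The plan states no figure to reproduce. The check is a comparison of readings followed by a short calendar calculation.

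**Step 1. What each reading records.** An ordinary grade 1 event here means one that is non-serious and leads to no treatment change. A qualifying event is one that meets any of the first three bullets.

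| Reading of the fourth bullet | Event | During dosing | Within 7 days after last dose | Later, to Day 42 |
|---|---|---|---|---|
| Literal: one of four alternatives | Ordinary grade 1 | No | Yes | No |
| | Qualifying | Yes | Yes | Yes |
| Time limit on the other three | Ordinary grade 1 | No | No | No |
| | Qualifying | Yes | Yes | No |
| Alternative that also covers the dosing days | Ordinary grade 1 | Yes | Yes | No |
| | Qualifying | Yes | Yes | Yes |

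The three readings give three different datasets. Only the first follows the words as they stand.

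**Step 2. Where the window closes.** Inputs:

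- Course length, from Enrollment: for hydroxychloroquine, "followed by 200mg twice a day for four consecutive days (Five days in total"). The other regimens are also five days.
- First dose on Day 0, where the Schedule of events first marks study drug. A five-day course then ends on Day 4.
- The same schedule marks study drug in six columns, Day 0 to Day 5, so the last dose could fall on Day 5. The two places need to be reconciled. Both days are carried here.
- Follow-up of 42 days, from Follow up.

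Window closes on: last dose day + 7.

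- Last dose Day 4: 4 + 7 = Day 11
- Last dose Day 5: 5 + 7 = Day 12

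**Step 3. What the limit reading would leave out.** Days uncovered: 42 − closing day.

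- 42 − 11 = 31 days, and 31/42 = 74%
- 42 − 12 = 30 days, and 30/42 = 71%

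The contacts on Days 21, 28, 35 and 42 all fall in this stretch. The Schedule of events marks both the adverse drug reaction row and the record review row at each of them. If the limit were also applied to serious events, it would conflict with the six-week period in Reporting Requirements.

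**Step 4. What the literal reading does.** No qualifying event is lost at any time. The distortion is confined to ordinary grade 1 events: they are excluded over the whole five-day course, included for seven days, then excluded again.

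**The case against.** The strongest reply is that the fourth bullet was meant as an outer limit that takes in the dosing days and still works as one alternative among four. All events would then be recorded to about Day 11 or 12, and qualifying events to the end of follow-up. This agrees with the Schedule of events and with Reporting Requirements. It does close the on-treatment gap, but it adds dosing days that the bullet does not mention, and it leaves the grade 2 threshold with nothing to do until about Day 11 or 12. A site could not be expected to infer it.

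Other parts of the reply do stand, and they rule out stronger readings that a reader might infer:

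- **That on-treatment grade 1 events are missed altogether.** Those that change treatment or are serious are recorded during dosing. Every reported event must also be graded, so the post-dose grade 1 events could be separated in a table. The missing on-treatment ones could not be recovered that way.
- **That 30 of 42 days of grade 2 or higher events are lost.** This arises only if *any* is overridden. As written, the first three bullets have no end date. The adverse drug reaction row is also narrower than adverse events in general. The record review row gives the broader support to Day 42.
- **That a window tied to the last dose biases the azithromycin comparison through early stopping.** Nothing in the documents indicates that stopping will differ by arm. On the literal reading the window stays seven days long and merely moves, for ordinary grade 1 events only.
- **That the first dosing day is unobserved.** The adverse drug reaction row is blank on Day 0, but record review is marked that day and covers both AEs and SAEs.

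**Conclusion.** The point holds for the recording rule as worded. Ordinary grade 1 events are recorded in the seven days after the last dose and not during the five-day course, and no other section corrects this. The rule thus gives an inconsistent account of mild toxicity, which is more than a missing detail.

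The size is limited. On the literal reading, qualifying events are unaffected, and serious events are separately covered for six weeks. The gap of 30 to 31 days (71% to 74% of follow-up) is conditional on the sponsor having meant the bullet as a limit, on a first dose on Day 0, and on a last dose on Day 4 or 5. The documents do not support a claim that either reading favors one arm. The primary endpoint is not touched. The rewording should be made because the defect lies in the rule itself and is cheap to remove.

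**What to change.** In Adverse Event Collection Requirements for this protocol, remove the fourth bullet from the list and state one fixed recording period for all arms: adverse events meeting any of the first three criteria, from randomization to Day 42. Randomization is the better anchor because Reporting Requirements already counts its six weeks from there, and because participants who are randomized but never dosed then also have a defined period. Day 42 is where the Schedule of events ends.

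If grade 1 events are wanted, add a separate sentence giving one period for them that includes the dosing days and is the same in all arms. Without that sentence, the rewording also ends the recording of ordinary grade 1 events in the week after dosing.

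Marking the adverse drug reaction row on Day 0 is an optional tidy-up.

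The cost is one reworded list, with no added contacts. If the sponsor had intended the limit reading, there will be somewhat more late events of grade 2 or higher to enter.
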